6.5.2 ADMINISTRATION OF VACCINE OR PLACEBO

Vaccine or placebo will be administered by blinded study staff given syringes labeled with the participant's study number, by the unblinded Pharmaceutical Operations team preparing injections. Each dose of PfSPZ Vaccine, PfSPZ Challenge and placebo will be administered in 0.5 mL by DVI into a vein in the participant's arm, wrist or hand using a needle and syringe according to SOP and the study schedule.

6.5.3 MODIFICATION OF STUDY INVESTIGATIONAL PRODUCT (IP) FOR A PARTICIPANT

Dosing of PfSPZ Vaccine or PfSPZ Challenge will be discontinued if found to be unacceptably reactogenic or unsafe for individual participants. If a participant experiences notable toxicity related to PfSPZ Vaccine, the investigators and the Sponsor, in consultation with the Local Safety Monitor and the SMC will determine if subsequent immunizations in that participant is acceptable or halted. If a participant experiences an SAE deemed to be related to PfSPZ Vaccine, the participant will not receive the relevant subsequent doses unless so recommended by the SMC, Sponsor, and PI.

6.5.4 ACCOUNTABILITY PROCEDURES FOR THE STUDY INVESTIGATIONAL PRODUCT

The site PI alone has the authority to distribute or dispose of the IP as instructed by Sanaria and is responsible for IP accountability. The site PI will normally delegate responsibility for IP accountability to the head of Pharmaceutical Operations so that he or she may remain blinded to treatment assignment. The site PI and designee will be responsible for maintaining complete records and documentation of IP, accountability, dispensation, temperature monitoring, storage conditions, and final disposition of the study product. All study IPs, whether administered or not, must be documented on the appropriate study IP accountability record or dispensing log.

Upon completion of each day of immunizations with PfSPZ Vaccine or injection with PfSPZ Challenge, any remaining unused study IP will be returned to the Sponsor according to the appropriate SOP(s).

6.6 MEASURES TO MINIMIZE BIAS: RANDOMIZATION AND BLINDING

6.6.1 RANDOMIZATION

On the day of first immunization (V1 = study day 1), each participant invited to enroll will be randomized to receive PfSPZ Vaccine or NS according to a 3:1 ratio with randomization blocked to assure an approximation of this ratio in each CHMI cohort.

In the situation where an eligible participant withdraws consent or is deemed to be ineligible after treatment assignment but prior to administration of the first dose (e.g. due to acute illness or a request to withdraw from participation), a back-up participant will be assigned the same randomization number in the place of the participant who has become ineligible or has withdrawn consent. The withdrawn participant will be considered a screening failure, and the replacement participant will assume the randomization number of the withdrawn participant in order to assure that the study group receives the correct number of vaccine and placebo assignments. Once an injection has been given, however, even if the study participant withdraws immediately thereafter, the randomization number will not be reused, and the individual will be considered a drop-out.

The randomization procedure will be conducted by the data management and statistics vendor for this trial, as described in the applicable SOPs. Access to the unblinded randomization list will be limited exclusively to the syringe preparation team and the independent statistician(s) at the data management vendor. These individuals will be unblinded and will not be involved in evaluation or care of the study participants. A copy of participant treatment assignments will be retained at the site in a secure file by the unblinded Pharmaceutical Operations staff.

6.6.2 UNBLINDING

Details of all unblinding procedures are provided in the unblinding SOP. An overview is provided here.

Study participants, clinical investigators (including the PI) and all other staff involved in measuring study outcomes will remain blinded to treatment allocation until the data from (at least) 28 days after CHMI are cleaned and locked. The site PI will be responsible for strict maintenance of the blind. Only the Pharmaceutical Operations team responsible for syringe preparation and the responsible statistician from the data management vendor will be unblinded from the onset of the trial.

The regulatory team and select members of the clinical team of the Sponsor, Sanaria, may be unblinded at any time if there is an urgent regulatory or research need for unblinded safety, tolerability or efficacy data. This will be discussed with the site PI and the plan approved before putting it into effect.

Unblinding of individual participants: If knowledge of the treatment assignment is needed to provide appropriate medical care, and unblinding is recommended by the PI, the Local Safety Monitor, or the SMC, the treatment assignment of that participant will be unblinded and provided to the PI on a need-to-know basis. The PI must contact the Sponsor and provide documentation of the event and the reasons for unblinding. If unblinding is required, the treatment assignment from the on-site secure file will be provided by the unblinded staff.

If pausing criteria are met based on blinded data, the PI will provide the list of participants contributing to pausing criteria and inform the head of the Pharmaceutical Operations team how many of these participants have to be vaccine recipients (as opposed to normal saline recipients) in order to truly meet pausing criteria. The head of the Pharmaceutical Operations team or designee will privately identify the

treatment assignment of each participant on the list, and then inform the PI if the pausing criteria have been met but will not unblind the PI with respect to individual volunteers unless necessary.

Information or correspondence that could unblind individuals who interact with volunteers, including the Sanaria clinical team and any others involved with syringe preparation, will be held confidential until the official unblinding. When syringes are being prepared or treatment allocation lists are exposed, access to the syringe preparation room will be restricted and staff who interact with the volunteers will not be permitted to enter.

Similarly, only the clinical team will interact with the research participants. The team preparing injections will not interact with participants.

However unlikely, any case of inadvertent or unauthorized unblinding will be reported to the Sponsor within 7 days and prior to performing any scheduled study procedures with the affected study volunteer(s). Evaluation and treatment of acute medical problems and any procedures related to safety may proceed, even if the inadvertent blinding has not yet been reported to the Sponsor.

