8.3.3.2 RELATIONSHIP TO STUDY INTERVENTION

The site PI or investigator must assign a relationship of each AE to the receipt of the investigational product. The investigator will use clinical judgment in conjunction with the assessment of a plausible biologic mechanism, a temporal relationship between the onset of the event in relation to receipt of the investigational product, and identification of possible alternate etiologies including underlying disease, concurrent illness or concomitant medications. The following guidelines should be used by investigators to assess the relationship of an AE to study product administration.

Not related: No relationship to investigational product. Applies to those events for which evidence exists that there is an alternate etiology.

Unlikely: Likely unrelated to the investigational product. Likely to be related to factors other than investigational product but cannot be ruled out with certainty.

Possible: An association between the event and the administration of investigational product cannot be ruled out. There is a reasonable temporal association, but there is an alternative etiology that is more likely.

Probable: There is a high likelihood that a relationship to the investigational product exists. There is a reasonable temporal association, and the event cannot be explained by known characteristics of the participant's clinical state or factors including other therapy. However, there are alternative explanations, even if less likely.

Definite: An association exists between the receipt of investigational product and the event. An association to other factors has been ruled out.

To convert these designations to a binary system, "not related" and "unlikely related" will be considered "unrelated" while "possibly related", "probably related" and "definitely related" will be considered "related."

The Sponsor will determine the final classification of relatedness and expectedness for an AE.

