9.2 SAMPLE SIZE DETERMINATION

The primary outcome for these studies will be VE measured as $[1 - \text{risk ratio}] \times 100$. The outcomes of both CHMI's will be combined. Sample sizes of 45 and 15 for the vaccine and placebo groups were selected to be able to show with 83% power, if there are six drop-outs from the vaccine group and two from the control group prior to CHMI, that an infection rate of 92.3% in the controls (12/13 developing parasitemia) and 51% in the vaccinees (20/39 developing parasitemia) is statistically significantly different ($\alpha=0.05$, 2-tailed) (VE=44.4%). As we expect VE to be higher than this, the sample size should be adequate.

Regarding safety, the study provides the following power to identify adverse outcomes:

1. If no PfSPZ Vaccine-related SAEs are observed, the sample size of 45 provides 95% confidence that the true rate of SAEs caused by immunization is less than 6.7%, 90% confidence that the true rate of SAE's is less than 5.0%, 85% confidence that the true rate of SAEs is less than 4.2%, and 80% confidence that the true rate of SAEs is less than 3.5%.
2. With regard to the ability to make comparisons between vaccinees and placebo recipients in the rates of grade 2 and grade 3 adverse events, where significant differences might indicate poor tolerability, a sample size of 45 vaccinees and 15 placebo recipients will show a statistically significant difference ($p<0.05$, two-tailed) between 10/45 vaccinees experiencing poor tolerability on the one hand, and 0/15 controls on the other hand.

Immunogenicity:

Antibody responses (group means, standard deviations, medians and ranges) will be used to compare participants with controls, and to compare infected and non-infected participants, the latter to look for trends suggesting a threshold response above which VE is seen, using appropriate nonparametric tests such as Wilcoxon and Spearman correlation. The data management vendor is providing biostatistical consultation and will generate the Statistical Analysis Plan, which will be finalized in advance of the database lock. The same vendor will conduct the statistical analyses.

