9.4.7 PLANNED INTERIM ANALYSIS

No formal interim analyses are planned.

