10.1.4 STUDY DISCONTINUATION AND CLOSURE

This study may be temporarily suspended or prematurely terminated if there is sufficient reasonable cause. If the study is suspended or terminated, the site PI will promptly inform the study participants, the IRB, and the Sponsor and will provide the reason(s) for the suspension or termination. Study participants will be informed of changes to the study visit schedule, as applicable.

Circumstances that may warrant termination or suspension include, but are not limited to:

- Determination of unexpected, significant, or unacceptable risk to participants
- Demonstration of efficacy that would warrant stopping
- Insufficient compliance to protocol requirements
- Data that are not sufficiently complete and/or evaluable

The study may resume once concerns about safety, protocol compliance, and data quality are addressed.

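### Section 6.6.2 allows early sponsor access to unblinded efficacy data with no named approver or firewall, while efficacy is a listed stopping reason and no interim look is planned

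*Combined protocol and SAP*

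**What the plan says.** **Who may see allocation.** Section 6.6.2 says the sponsor's regulatory team and select members of its clinical team "may be unblinded at any time if there is an urgent regulatory or research need for unblinded safety, tolerability or efficacy data". The condition follows: "This will be discussed with the site PI and the plan approved before putting it into effect". The text does not say who approves, on what criteria, what is recorded, or what an unblinded person may no longer do.

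**Who may not.** Section 6.6.1 gives the unblinded list to the syringe preparers and the vendor's independent statisticians and to nobody else. Near its end, 6.6.2 itself says that unblinding information is kept confidential until the official unblinding. It names the sponsor's clinical team in that sentence.

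**When the blind is lifted.** Participants, investigators and outcome staff "will remain blinded to treatment allocation until the data from (at least) 28 days after CHMI are cleaned and locked". The sentence does not mention the sponsor's teams, and does not say that both challenge cohorts must be locked.

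**Looks and stopping.** Section 9.4.7: "No formal interim analyses are planned". Section 10.1.4 lists, among circumstances that may justify suspending or ending the study, "Demonstration of efficacy that would warrant stopping". It gives no boundary and no decision-maker. Section 9.2 sets one two-tailed alpha of 0.05.

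**Decisions open to the sponsor.** Section 8.3.3.2: "The Sponsor will determine the final classification of relatedness and expectedness for an AE". The primary safety endpoint (Synopsis and 3.2) counts related events. The SAP need only be final before database lock (9.2), may differ in minor ways from the protocol, and sponsor collaborators take part in the analysis (9.4.1). Section 9.3.4 removes participants who stray significantly from procedures from the primary efficacy analysis, without naming who decides.

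**The concern.** Each provision is tolerable alone; together they leave a gap. Efficacy by arm can be seen early and can be a reason to stop, with no statistical rule for either. The people who may see it belong to the organisation that settles final relatedness, contributes to the analysis, and can influence an SAP that is not yet final. With about 13 controls in the primary comparison, a few exclusions or a late choice of test could matter. Section 9.4.3 does not clearly name the primary test: Fisher's exact test appears under the secondary analysis.

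An early look is also practical. qPCR results are acted on as they arrive, so adding allocation gives efficacy at once. The 3-week cohort is about half the trial. All vaccine dosing ends on day 29, so an efficacy stop would in practice mean not challenging, or not following, the rest of the 12-week cohort.

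**Working it through.** **1. Is any alpha held back?** Inputs from 9.2: 12/13 = 0.923 infected controls, 20/39 = 0.513 infected vaccinees, two-sided 0.05.

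- VE = 1 − 0.513/0.923 = 44.4%, as stated.
- Pooled rate = 32/52 = 0.615; difference = 0.410.
- Null SE = √[0.615 × 0.385 × (1/13 + 1/39)] = 0.156.
- Alternative SE = √[0.923 × 0.077/13 + 0.513 × 0.487/39] = 0.109.
- Power = Φ[(0.410 − 1.96 × 0.156)/0.109] = 83.2%.

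The stated 83% reproduces as a single test at the full 0.05, so nothing is reserved for an early decision.

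**2. What would an unadjusted look do?** Assume one look after the 3-week cohort (information fraction about 0.5; 4.2 splits the sample roughly in half), tested at 0.05, with freedom to stop or claim efficacy, followed by the final test at 0.05.

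Normal theory, correlation √0.5 = 0.707: 1 − P(|Z₁| < 1.96 and |Z₂| < 1.96) = 8.3%. At fractions 0.25 and 0.75 it is 9.1% and 7.3%.

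Exact enumeration, with 7 controls and 20 vaccinees at the look and 13 and 39 at the end:

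| Common infection rate | Fisher, one test → two looks | Uncorrected chi-square, one test → two looks |
|---|---|---|
| Worst case over all rates | 3.4% → 5.1% | 5.3% → 8.4% |
| 92.3% (planned control rate) | 1.8% → 2.1% | 2.9% → 4.3% |
| 96.4% (27/28 historical rate, 3.1) | 0.62% → 0.65% | 2.2% → 2.7% |

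The two-look chi-square maximum falls near a 62% infection rate and the Fisher maximum near 32%, both far from what the protocol expects under the null.

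**3. Is there time for a look?** From 8.2.3.1, the 3-week cohort is challenged on day 50 and completes on day 78 (50 + 28). The 12-week cohort is challenged on day 113 and completes on day 141. The gap from first results to second challenge is 113 − 78 = 35 days; from first results to last results it is 141 − 78 = 63 days. These are participant study days. They are calendar gaps only if the cohorts enrol together, and the Synopsis plans 3 months of recruitment.

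**4. Passages side by side.** Section 6.6.1 makes list access exclusive. The end of 6.6.2, on its plainest reading, keeps unblinding information from the sponsor's clinical team. The middle of 6.6.2 permits select members of that team to be unblinded. No sentence says which rule gives way.

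**The case against.** The permission is not open-ended. The need must be urgent, only select clinical staff are covered, the site investigator is consulted, and a plan must be approved. Section 6.6.2 describes itself as an overview of an unblinding SOP that is not among the documents and may say more. This narrows the permission, but the protocol still names no approver and no firewall, and does not define a research need.

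Four stronger readings are tempting, and the documents do not support them.

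- *The type I error is 8.3%.* Seeing data does not by itself inflate alpha; an early stop or claim does, and none is planned. The figure is a large-sample approximation. With Fisher's test the exact worst case is 5.1%, and at the planned infection rate both tests stay below 5%.
- *The double blind for safety fails.* Blinded investigators assign relatedness first. Under 4.1, unsolicited collection after vaccination ends 21 or 28 days after the third dose (day 50 or 57), about when challenge PCR begins. Section 9.4.4 also compares AE rates without limiting them to related events. What stands is that the sponsor's final classification has no date and no blinding condition.
- *The study may be unblinded once the 3-week cohort is locked.* Section 3.1 computes VE once every participant's outcome is known and the study is unblinded, which implies a single unblinding. Section 6.6.2 is merely unclear.
- *Inclusion of mid-challenge drop-outs is free judgement.* Section 9.3.4 gives a rule: a positive PCR counts as not protected; a negative counts only if it falls on or after the latest positive day among the others. The discretion that remains concerns exclusions for straying from procedures.

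The qPCR endpoint is objective, and positives are reconfirmed at an outside laboratory (8.2.3.4), so measurement bias is not the issue.

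**Conclusion.** The point holds as a gap in control, not as demonstrated bias or demonstrated inflation. The protocol permits early sponsor sight of efficacy by arm, contradicts itself on who may have it, lists efficacy as a stopping reason without a rule, and does not keep unblinded staff out of relatedness, SAP or exclusion decisions. Freedom from bias and the 5% error rate are therefore not assured.

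The possible inflation runs from negligible to 8.4%. It depends on three things: that an unadjusted look leads to a stop or claim, which test is used, and the infection rate. Bias through relatedness or exclusions cannot be sized from the documents. The timing assumes that the cohorts enrol together, and nothing here accounts for what the SOP or a separate SAP may add. This is worth correcting because the correction is cheap.

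**What to change.** 1. In 6.6.2, strike 'or research' and 'or efficacy' from the sponsor sentence. Alternatively, keep it and bar anyone unblinded early from final relatedness classification, SAP content and population-inclusion decisions. In either case, name the approver.
2. Reconcile 6.6.1 with both parts of 6.6.2, so that one rule governs sponsor access.
3. State that general unblinding follows lock of day-28 data from both challenge cohorts, in line with 3.1.
4. Delete the efficacy item from the list in 10.1.4.
5. Finalise relatedness and the SAP before any sponsor unblinding. Striking words under item 1 still leaves early unblinding to safety data. If that must come first, someone who has not seen allocation should classify the remaining events.

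All of this is protocol wording. The cost is that the sponsor gives up early sight of efficacy, by at most about two months (63 days) if the cohorts enrol together. If the sponsor wants that look, it should be a planned one. O'Brien-Fleming levels of 0.0052 and 0.048 leave Fisher power at 79.5%, the same as one test at 0.05, and lower chi-square power from 85.1% to 82.8%.

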6.7 STUDY INTERVENTION COMPLIANCE

The investigational product will be administered via DVI by study staff. For participants who become parasitemic, anti-malarials will be administered by DOT.

6.8 CONCOMITANT MEDICATIONS/TREATMENTS

This protocol places no restrictions on the use of concomitant medications with the exception of the immunomodulators as detailed in the exclusion criteria, drugs with anti-malarial properties (e.g., doxycycline, clindamycin, azithromycin, trimethoprim/sulfamethoxazole) and drugs that might interfere with anti-malarials during the treatment phase post-CHMI in those participants who become parasitemic. Any pre-existing conditions that require routine or intermittent medications should be discussed at the time of screening and a study physician will determine if participation is safe and will not interfere with any data being collected. All concomitant medications received within 28 days before signing the consent should be recorded. Concomitant medications include prescription, over the counter and herbal medications and supplements.

Any new medications required during the course of participation in the study must be discussed with the study team to ensure both safety of the participant and integrity of the data being collected. Information regarding all over-the-counter and/or prescription medications taken will be collected and recorded at each scheduled study visit.

The investigator will recommend medication for symptomatic relief, if necessary. This will not affect the data collected from participants who take medication during the trial.

7. STUDY INTERVENTION DISCONTINUATION AND PARTICIPANT DISCONTINUATION / WITHDRAWAL

7.1 DISCONTINUATION OF STUDY INTERVENTION

The study intervention will be paused or discontinued if specified criteria in Sections 7.2 'Pausing Criteria, Unblinding and Safety Hold' or 7.3 'Temporary Hold of Immunization or CHMI of Individual Participants' are met (see below). Discontinuation from immunization does not mean discontinuation from the study, and remaining study procedures related to safety should be completed. Remaining study procedures related to research assays, such as collecting samples for immunology tests, may be continued if the participant agrees and the tests will provide meaningful data.

If a clinically significant finding is identified in a study participant after enrollment, the investigator will determine if any change in participant management is needed. This may involve a temporary suspension of the study intervention for an individual participant (e.g. delaying immunization until an acute illness has resolved) or for all participants (the latter after consultation with the Sponsor). The reason for pausing or discontinuation will be recorded on the Case Report Form (CRF) and any additional supplemental clinical notes that are required for complete documentation.

